### **10 SAFETY ANALYSES**

#### **10.1** Overview of Safety Analysis Methods

All safety and tolerability analyses will be performed on the safety population, consisting of all randomized and treated patients regardless of inclusion/exclusion violations, and summarized by the treatment actually received.

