Because randomization occurred prior to scheduling the surgery, some randomized patients did not receive surgery. Also, during surgery some patients were determined by the surgeon to be inappropriate candidates to receive the randomized surgery due to anatomic or other contraindications discovered at the time of the surgery and undeterminable prior to surgery. In these cases, the surgeon selected amongst the other two study surgeries based on physician preference.

Evaluations for superiority will follow a modified intent-to-treat (MITT) approach, and evaluations of non-inferiority will follow a per-protocol approach, which is the customary conservative approach for non-inferiority hypotheses.

To define the MITT population, the intent-to-treat population is modified to remove patients who were randomized but never received surgery due to patient-specific reasons unrelated to the randomized treatment.

The per-protocol population is the subset of the modified intent-to-treat population excluding all major protocol violations related to study treatment including receipt of a treatment other than the randomized treatment.

Safety data will be evaluated for the safety population that will exclude randomized participants who discontinued the study without having surgery and participants who received a non-study surgery rather than one of the three study surgeries. Treatment switchers will be included in the treatment they received.

M.3. Statistical Data Analysis

Both for the overall global test across cohorts and within each of the three cohorts, surgical failure rates will be compared using survival analysis approaches appropriate for interval censored data (e.g. interval censored piecewise proportional hazards models) and secondary outcomes will be reported as rates in each group or as group means and evaluated

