#### 5 ANALYSIS POPULATIONS

Because randomization occurred prior to scheduling the surgery, some randomized patients did not receive surgery. Also, during surgery some patients were determined by the surgeon to be inappropriate candidates to receive the randomized surgery due to anatomic or other contraindications discovered at the time of the surgery and undeterminable prior to surgery. In these cases, the surgeon selected amongst the other two study surgeries based on physician preference.

Evaluations for superiority will follow a modified intent-to-treat (MITT) approach, and evaluations of non-inferiority will follow a per-protocol approach, which is the customary conservative approach for non-inferiority hypotheses.

To define the MITT population, the intent-to-treat population (all randomized participants) is modified to remove patients who were randomized but never received surgery.

The per-protocol population is the subset of the modified intent-to-treat population excluding all major protocol violations related to study treatment, which might be receipt of a treatment other than the randomized treatment and might be another type of violation.

In addition, given that some patients received a treatment selected by the physician when their randomized treatment was contra-indicated, the MITT and Per-protocol populations were further refined so that treatment switches that were conservative against the null hypothesis are included in the population, and treatment switches that might make the comparison biased against the null are excluded (see below).

Safety data will be evaluated for the safety population that will exclude randomized participants who discontinued the study without having surgery. Participants who received an alternate surgery (treatment switch) after an intraoperative complication or medical contraindication or received a type of surgery other than one of the 3 study treatments will be presented by their randomized (index) surgery. Participants whose treatment was switched prior to surgery or very early during surgery with no initial intraoperative complication caused by the randomized (index) surgery or medical contraindication for the selected surgery (i.e. participant refusal or accidental switch) will be presented by their switched final procedure they received in safety displays. Such participants will be identified by study PI review prior to database lock.

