### **Online Supplement**

eFigures 1-3. Diagram of each of the 3 surgical procedures

eFigure 4. Pelvic Organ Prolapse Quantification (POPQ) Schematic

eTable 1 Analysis Populations and Visit Completion - All Randomized Participants

eTable XX follow-up durations and COVID timing by calendar time of enrollment

eTable 1A Data Collection/Completeness of Primary Efficacy by Randomized Treatment Group

eTable 1B Primary Outcome (First Event Incorporated) Completeness by Randomized Treatment Group

eFigure Y. Failure Probability for the Primary Outcome in the Per-Protocol Population

eFigure Z. Failure Probability for the Primary Outcome in the MITT-Narrow

eFigure 9. Distribution of Surgical Failure Outcome among Participants with Intermittent Failures in the Modified Intent-to-Treat Population

eFigure 4. Assumption Check: Smoothed Hazard Rates for the Primary Outcome

eFigure 5. Assumption check: Estimated Log Cumulative Hazard by Log-Time for the Primary Outcome

eTable X. Sensitivity Analysis: Failure Probability for the Primary Outcome in primary populations with further reduction of patients enrolled after FDA order to stop mesh.

eTable X. Sensitivity Analysis: Unadjusted Failure Probability for the Primary Outcome

eTable X. Sensitivity Analysis: Failure Probability for the Primary Outcome adjusting for enrollment cohort

eTable X. Sensitivity Analysis: Hazard Ratio for the Primary Outcome with Random Site Effect

eTable 2 Concomitant procedures in the Modified Intent-to-Treat Population

eTable 3 Perioperative outcomes in the Modified Intent-to-Treat Population

eTable 4. Sexual Function and Dyspareunia Results from PISQ-IR a in the Modified Intent-to-Treat Population by Randomized Intervention

eTable 5. Adverse Events by System Organ Class and Preferred Term in Safety Population by Received Surgical Intervention

eTable 6. Serious Adverse Events by System Organ Class and Preferred Term in Safety Population by Received Surgical Intervention

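### SAP sections 5 and 10.1 put women switched after an intraoperative complication or contraindication in different arms for safety, and women given a non-study surgery are handled in three ways

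*SAP*

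**What the plan says.** **SAP section 5** splits the switchers.

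- "Participants who received an alternate surgery (treatment switch) after an intraoperative complication or medical contraindication" are placed with the arm to which they were allocated: they "will be presented by their randomized (index) surgery". The same sentence covers women given a type of surgery "other than one of the 3 study treatments will be presented by their randomized (index) surgery".
- Women switched before the operation or in its opening stage, with no complication from the index surgery and no contraindication (refusal or a mistake, for example), "will be presented by their switched final procedure they received in safety displays". The study PI identifies them before database lock.

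The definition of the safety population and the closing note on safety evaluations, both in section 5, repeat that only some switchers are shown as treated. That note also says that every safety analysis uses the safety population.

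**SAP section 10.1** says that all safety and tolerability analyses are "summarized by the treatment actually received". It makes no exception and does not point to section 5.

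**SAP section 14** titles eTable 5 "Adverse Events by System Organ Class and Preferred Term in Safety Population by Received Surgical Intervention", and eTable 6 does the same for serious events. Table 2, which includes safety and tolerability outcomes, and eTable 3, on perioperative outcomes, are placed in the MITT population.

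**Protocol M.2** says "Treatment switchers will be included in the treatment they received" and removes from the safety population "participants who received a non-study surgery rather than one of the three study surgeries".

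**The concern.** The analyst has two instructions for the same woman. Suppose that she is allocated to sacral colpopexy, has an intraoperative complication, and leaves the operating room with a native tissue repair. Section 5 counts her event against sacral colpopexy. Section 10.1, read literally, counts it against native tissue, so an event arising during one operation is charged to the operation that replaced it.

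Both SAP section 5 and protocol M.2 explain switches during surgery by contraindications found at operation, so the women on whom the rules disagree belong to a group that the plan expects to exist. Comparing safety across the three procedures is a stated secondary aim. One manuscript could show the same woman under different arms in different tables.

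A related problem affects prolapse mesh exposure. A woman switched from a mesh arm to native tissue has no prolapse mesh to become exposed, yet the section 5 rule leaves her in the mesh arm's denominator.

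**Working it through.** **1. Arm assigned under each rule**

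| Woman | SAP 5 | SAP 10.1, eTables 5 and 6 | Protocol M.2 | Table 2, eTable 3 (MITT) |
|---|---|---|---|---|
| Switched after an intraoperative complication or contraindication | Randomised | Received | Received | Randomised |
| Switched before or very early in surgery, neither present | Received | Received | Received | Randomised |
| Given a non-study surgery | Randomised | No arm exists | Excluded | Randomised |

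Only the second row agrees across section 5, section 10.1 and protocol M.2, and there the MITT displays differ. SAP section 5 says that the safety and MITT populations contain the same women, so the MITT displays differ from the section 5 rule only in the arm given to these early switchers.

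**2. Size of the effect (illustration)**

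The plan states no figure to reproduce, and the documents give no switcher count. Inputs:

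- 121 women per arm (SAP section 6).
- k = 6 switchers from sacral colpopexy (SC) to native tissue (NT). Six is the count at which SAP section 5 runs its sensitivity analyses. It is not a forecast.
- Assumed background: 12 events among the other 115 SC women (10.4%) and 12 among the 121 NT women (9.9%).
- c = number of switchers with a complication.

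Formulas for SC minus NT:

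- By index surgery: (12 + c)/121 - 12/121.
- By surgery received: 12/(121 - k) - (12 + c)/(121 + k).

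| Case | By index surgery | By surgery received | Swing (points) |
|---|---|---|---|
| k = 6, c = 6 | 18/121 - 12/121 = +5.0 | 12/115 - 18/127 = -3.7 | 8.7 |
| k = 6, c = 3 | 15/121 - 12/121 = +2.5 | 12/115 - 15/127 = -1.4 | 3.9 |
| k = 6, c = 0.6 (10% of 6) | 12.6/121 - 12/121 = +0.5 | 12/115 - 12.6/127 = +0.5 | about 0 |
| k = 1, c = 1 (12 events among the other 120 SC women) | 13/121 - 12/121 = +0.8 | 12/120 - 13/122 = -0.7 | 1.5 |

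The swing depends on how many women switch and on how far their complication risk exceeds that of the other women.

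**3. Mesh-exposure denominator**

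The prolapse mesh-exposure indicators in SAP section 10.2 give a zero to any woman with a post-operative visit and responses recorded as not evident. They do not require that she received prolapse mesh. If 6 of 121 women in a mesh arm have none, the observed rate is the true rate times 115/121 = 0.950, a relative dilution of about 5%. A true 5.0% would appear as about 4.8%. This assumes that the form records not evident for a woman without mesh.

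**The case against.** The best defence is that section 5 is the detailed definition, stated three times and tied to a review before database lock. Section 10.1 is a one-sentence overview of a population that section 5 defines, so it probably was not updated. That is a fair account of how the conflict arose, and it supports keeping the section 5 rule. It does not remove the conflict: the SAP does not say that section 5 prevails, and protocol M.2 and the titles of eTables 5 and 6 agree with section 10.1. SAP section 14 lets displays change without amendment only where they do not contradict the SAP text.

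Four stronger readings are tempting, and the documents do not support them.

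- A reader might infer that section 5 sends all switchers to the randomised arm. It does not; early switches with no complication or contraindication go to the surgery received.
- A reader might take 8.7 points as the expected effect. It requires six switchers, all in one direction and all with a complication. The section 5 rule also covers contraindications without a complication, and nothing in the documents gives the complication rate among switchers.
- A reader might extend the denominator problem to mesh erosion. The prolapse mesh-erosion indicator is already limited to women whose surgeon's report records Uphold LITE.
- A reader might set the swing against the protocol's 15-point difference. Protocol N.4 offers that figure to guide the DSMB on a defined set of important complications. It is not a benchmark for the final safety tables.

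**Conclusion.** The conflict is real but limited to two groups: women switched after an intraoperative complication or contraindication, and women given a non-study surgery. For the first, the choice of text decides which operation is charged with the event. For the second, the protocol and SAP disagree on whether they are analysed at all, and section 10.1 gives them no arm. The MITT placement of Table 2 and eTable 3 adds an inconsistency with section 5 itself.

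The effect on results cannot be stated from the documents. Under the assumptions above it runs from about zero to 8.7 points with six switchers, and the sign of the difference can reverse when switchers carry an excess of complications. The mesh-exposure dilution is modest. The section 5 rule is defensible in itself, because it keeps an index surgery's complication with that surgery. What is wrong is that the rest of the plan does not follow it.

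**What to change.** - Make section 5 the single governing rule and replace the received-treatment wording in section 10.1 with a reference to it.
- Put the safety rows of Table 2 and all of eTable 3 in the safety population, and retitle eTables 5 and 6 to match.
- Record the departure from protocol M.2, with one stated handling of non-study surgeries.
- Restrict the prolapse mesh-exposure denominator to women who received prolapse mesh.
- List switchers individually, with allocated surgery, surgery received, reason and arm used.
- Report the as-received assignment as a sensitivity display. This also shows exposure under the mesh actually placed for any woman switched between the two mesh operations.

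Keeping the section 5 rule avoids choosing a new one late: SAP section 12 already reports primary-outcome events by arm, so any further change should be dated and labelled accordingly. The cost is a small amount of programming and one extra table.

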## **10.2** Safety and Tolerability Variables

Variable	CRF Source	Туре	Timepoint(s)	Definition
Secondary Safety and Toler	ability Outcon	mes		
Indicator of prolapse mesh exposure in the anterior vagina	CRF-8, CRF- 10/12, AE log	Binary	Post-surgery through last visit	
 
Through the timepoint of follow-up, the indicator is defined as follows:
 
1 = Yes, if mesh exposure in vagina is reported as evident (i.e. response of "AE", "SAE") and Anterior=Yes and Description of Management of Mesh Exposure indicates the mesh was "from/for Prolapse Surgery" (case insensitive) on any of the complication tables as described above
 
0 = No, else if subject attended at least one post-operative visit 6 weeks or after and complication(s) of interest specified above are reported as "Not Evident" across all attended post-operative visits. Subjects with missing responses are included as long as the subject has at least one "Not Evident" response (assuming low missing response rate among attended visits).
 
. = Missing, otherwise
 

Indicator of prolapse mesh exposure in the posterior vagina	CRF-8, CRF- 10/12, AE log	Binary	Post-surgery through last visit	
 
Through the timepoint of follow-up, the indicator is defined as follows:
 
1 = Yes, if mesh exposure in vagina is reported as evident (i.e. response of "AE", "SAE") and Posterior=Yes and Description of Management of Mesh Exposure indicates the mesh was "from/for Prolapse Surgery" (case insensitive) on any of the complication tables as described above
 
0 = No, else if subject attended at least one post-operative visit 6 weeks or after and complication(s) of interest specified above are reported as "Not Evident" across all attended post-operative visits. Subjects with missing responses are
 

				<pre>included as long as the subject has at least one "Not Evident" response (assuming low missing response rate among attended visits).</pre> . = Missing, otherwise
exposure in the distal (lower half/introitus) vagina	CRF-8, CRF- 10/12, AE log	Binary	Post-surgery through last visit	Through the timepoint of follow-up, the indicator is defined as follows:         1 = Yes, if mesh exposure in vagina is reported as evident (i.e. response of "AE", "SAE") and distal (lower half/introitus)=Yes and Description of Management of Mesh Exposure indicates the mesh was "from/for Prolapse Surgery" (case insensitive)         on any of the complication tables as described above
				0 = No, else if subject attended at least one post-operative visit 6 weeks or after and complication(s) of interest specified above are reported as "Not Evident" across all attended post-operative visits. Subjects with missing responses are included as long as the subject has at least one "Not Evident" response (assuming low missing response rate among attended visits).
Indicator of prolapse mesh exposure in the apex of vagina	CRF-8, CRF- 10/12, AE log	Binary	Post-surgery through last visit	
 
Missing, otherwise
 
Through the timepoint of follow-up, the indicator is defined as follows:
 
1 = Yes, if mesh exposure in vagina is reported as evident (i.e. response of "AE", "SAE") and apex=Yes and Description of Management of Mesh Exposure indicates the mesh was "from/for Prolapse Surgery" (case insensitive) on any of the complication tables as described above
 

				0 = No, else if subject attended at least one post-operative visit 6 weeks or after and complication(s) of interest specified above are reported as "Not Evident" across all attended post-operative visits. Subjects with missing responses are

				<pre>included as long as the subject has at least one "Not Evident" response (assuming low missing response rate among attended visits).</pre> . = Missing, otherwise
Indicator of prolapse mesh erosion (exposure into adjacent organs)	CRF-8, CRF- 10/12, AE log	Binary	Post-surgery through last visit	Through the timepoint of follow-up among subjects who received the hysteropexy surgical intervention as reported on the surgeon's report CRF-8 (i.e. response to question A8 is "Uphold Lite"), based on the systematic collection of open-ended adverse events as reported on the AE log with an onset start date on or after the date of surgical intervention and based on the specific complications as reported on the evaluator (blinded) follow-up CRF-10/12 collected at 6-weeks and in 6-month intervals through 5 years, the indicator is defined as follows:
				1 = Yes, if mesh erosion into viscera (urethra, bladder, ureter, rectum, or bowel locations) is reported as evident (i.e. response of "AE", "SAE") on any of the complication tables as described above
				0 = No, else if subject attended at least one post-operative visit 6 weeks or after and complication(s) of interest specified above are reported as "Not Evident" across all attended post-operative visits. Subjects with missing responses are included as long as the subject has at least one "Not Evident" response (assuming low missing response rate among attended visits).
				. = Missing, otherwise
Indicator of midurethral sling (MUS)mesh exposure in the anterior vagina	CRF-8, CRF- 10/12, AE log	Binary	Post-surgery through last visit	Through the timepoint of follow-up, the indicator is defined as follows: 1 = Yes, if mesh exposure in vagina is reported as evident (i.e. response of "AE", "SAE") and Anterior=Yes and Description of Management of Mesh Exposure indicates the mesh was "from/for sling" (case insensitive)

				on any of the complication tables as described above 0 = No, else if subject attended at least one post-operative visit 6 weeks or after and complication(s) of interest specified above are reported as "Not Evident" across all attended post-operative visits. Subjects with missing responses are included as long as the subject has at least one "Not Evident" response (assuming low missing response rate among attended visits). . = Missing, otherwise
Indicator of midurethral sling (MUS)mesh exposure in the posterior vagina	CRF-8, CRF- 10/12, AE log	Binary	Post-surgery through last visit	
 
Through the timepoint of follow-up, the indicator is defined as follows:
 
1 = Yes, if mesh exposure in vagina is reported as evident (i.e. response of "AE", "SAE") and Posterior=Yes and Description of Management of Mesh Exposure indicates the mesh was "from/for sling" (case insensitive) on any of the complication tables as described above
 
0 = No, else if subject attended at least one post-operative visit 6 weeks or after and complication(s) of interest specified above are reported as "Not Evident" across all attended post-operative visits. Subjects with missing responses are included as long as the subject has at least one "Not Evident" response (assuming low missing response rate among attended visits).
 
. = Missing, otherwise
 

Indicator of midurethral sling (MUS)mesh exposure in the distal (lower half/introitus) vagina	CRF-8, CRF- 10/12, AE log	Binary	Post-surgery through last visit	Through the timepoint of follow-up, the indicator is defined as follows: 1 = Yes, if mesh exposure in vagina is reported as evident (i.e. response of "AE", "SAE") and distal (lower half/introitus)=Yes and Description of Management of Mesh Exposure indicates the mesh was "from/for sling" (case insensitive)

				on any of the complication tables as described above 0 = No, else if subject attended at least one post-operative visit 6 weeks or after and complication(s) of interest specified above are reported as "Not Evident" across all attended post-operative visits. Subjects with missing responses are
				included as long as the subject has at least one "Not Evident" response (assuming low missing response rate among attended visits).
				. = Missing, otherwise
Indicator of midurethral sling	CRF-8,	Binary	Post-surgery	Through the timepoint of follow-up, the indicator is defined as follows:
(MUS)mesh exposure in the apex of vagina	CRF- 10/12, AE log		through last visit	1 = Yes, if mesh exposure in vagina is reported as evident (i.e. response of "AE", "SAE") and apex=Yes and Description of Management of Mesh Exposure indicates the mesh was "from/for sling" (case insensitive)
				on any of the complication tables as described above
				0 = No, else if subject attended at least one post-operative visit 6 weeks or after and complication(s) of interest specified above are reported as "Not Evident" across all attended post-operative visits. Subjects with missing responses are included as long as the subject has at least one "Not Evident" response (assuming low missing response rate among attended visits).
				. = Missing, otherwise
Indicator of midurethral sling (MUS) mesh erosion (exposure into adjacent organs)	CRF-8, CRF- 10/12, AE log	Binary	Post-surgery through last visit	Through the timepoint of follow-up among subjects who received transobturator or retropubic midurethral sling as reported on the surgeon's report CRF-8 (i.e. questions E1 or E2 is "Yes" for performed), based on the systematic collection of open-ended adverse events as reported on the AE log with an onset start date on or after the date of surgical intervention and based on the specific complications as reported on the evaluator

				(blinded) follow-up CRF-10/12 collected at 6-weeks and in 6-month intervals through 5 years, the indicator is defined as follows:
				1 = Yes, if mesh erosion into viscera (other specified location containing "sling") is reported as evident (i.e. response of "AE", "SAE") on any of the complication tables as described above or on the AE log identified by the AE verbatim term containing "mus mesh erosion" (case insensitive)
				If subject did NOT receive hysteropexy surgical intervention as reported on the surgeon's report CRF-8 (i.e. response to question A8 is "Uphold Lite"), then mesh erosion into viscera (urethra, bladder, ureter, rectum, bowel, or other specified locations) reported as evident (i.e. response of "AE", "SAE") on any of the complication tables as described above are also included as there are no other sources of mesh.
				0 = No, else if subject attended at least one post-operative visit 6 weeks or after and complication(s) of interest specified above are reported as "Not Evident" across all attended post-operative visits. Subjects with missing responses are included as long as the subject has at least one "Not Evident" response (assuming low missing response rate among attended visits).
				. = Missing, otherwise
				*Note: See above masked review note specified for outcome Indicator of hysteropexy mesh exposure.
Change from baseline in surgical pain scale SPS rest subscale score**	SPS	Continuous	6-weeks thru last visit	The SPS rest subscale score will be computed at baseline and at each timepoint's corresponding attended post-operative visit during which assessments are administered and collected using standard scoring algorithms (Barber 2012). Specifically, score the response for question Q1 (0=no pain sensation,, 10=most intense pain imaginable). If the

				question is missing a response, then the score is not calculated. The outcome will then be computed as the difference in score at each timepoint's corresponding attended post-operative visit and the score at baseline. If data for the assessment are missing at a timepoint's corresponding attended post-operative visit, the outcome variable will be coded as missing.
Change from baseline in surgical pain scale SPS normal activities subscale score**	SPS	Continuous	6-weeks thru last visit	The SPS normal activities subscale score will be computed at baseline and at each timepoint's corresponding attended post-operative visit during which assessments are administered and collected using standard scoring algorithms (Barber 2012). Specifically, score the response for question Q2 (0=no pain sensation,, 10=most intense pain imaginable). If the question is missing a response, then the score is not calculated. The outcome will then be computed as the difference in score at each timepoint's corresponding attended post-operative visit and the score at baseline. If data for the assessment are missing at a timepoint's corresponding attended post-operative visit, the outcome variable will be coded as missing.
Change from baseline in surgical pain scale SPS exercise subscale score**	SPS	Continuous	6-weeks thru last visit	The SPS exercise subscale score will be computed at baseline and at each timepoint's corresponding attended post-operative visit during which assessments are administered and collected using standard scoring algorithms (Barber 2012). Specifically, score the response for question Q3 (0=no pain sensation,, 10=most intense pain imaginable). If the question is missing a response, then the score is not calculated. The outcome will then be computed as the difference in score at each timepoint's corresponding attended post-operative visit and the score at baseline. If data for the assessment are missing at a timepoint's corresponding attended post-operative visit, the outcome variable will be coded as missing.
Change from baseline in surgical pain scale SPS worst pain subscale score**	SPS	Continuous	6-weeks thru last visit	The SPS worst pain subscale score will be computed at baseline and at each timepoint's corresponding attended post-operative visit during which assessments are administered and collected using standard scoring algorithms (Barber 2012). Specifically, score the response for question Q4

				(0=not bad at all,, 10=most intense bad feeling imaginable). If the question is missing a response, then the score is not calculated. The outcome will then be computed as the difference in score at each timepoint's corresponding attended post-operative visit and the score at baseline. If data for the assessment are missing at a timepoint's corresponding attended post-operative visit, the outcome variable will be coded as missing.
Change from baseline in body part pain score BPPS score**	SPS	Continuous	6-weeks thru last visit	The BPPS score will be computed at baseline and at each timepoint's corresponding attended post-operative visit during which assessments are administered and collected using standard scoring algorithms (TOMUS study). Specifically, average the responses for questions Q1 through Q7 (0=no or yes: no pain,, 10=yes: most intense). If there are missing responses, then the score is the average of the non-missing responses. The outcome will then be computed as the difference in score at each timepoint's corresponding attended post-operative visit and the score at baseline. If data for the assessment are missing at a timepoint's corresponding attended post-operative visit, the outcome variable will be coded as missing.
Maximum modified Dindo score across all complications And indicator for the Maximum modified Dindo score ≥ grade III	CRF-8, CRF-9, CRF- 10/12, CRF-11, CRF-13	Ordinal Categorical (11 levels)	6-weeks thru last visit	Through the timepoint of follow-up, based on the single Dindo score for the most severe complication as reported on the surgeon's report (unblinded) CRF-8, hospitalization CRF-9, evaluator (blinded) follow-up CRF-10/12 collected during surgery, during hospitalization, and at 6- weeks and in 6-month intervals through 5 years respectively, and as reported on the coordinator post-operative CRF-11, and coordinator follow-up CRF-13 collected at 6-weeks, and in 6-month intervals through 5 years respectively, the maximum of the Dindo scores (0.0=no complications, 1.0=grade I, 2.1=grade IIa, 2.2=grade IIabx, 2.3=grade IIb, 3.1=grade IIIo, 3.2=grade IIIa, 3.3=grade IIIb, 4.1=grade IVa, 4.2=grade IVb, 5.0=grade V) is taken excluding Dindo scores reported for granulation tissue, suture exposure, and/or suture erosion complications reported ≤ 12 weeks from surgical intervention (i.e. surgery and 6-week visits) on any of the complication tables as described above.

				If a subject reported no complications, then their maximum Dindo score will be assigned a value of 0.0=no complication. A missing maximum Dindo score is assigned to subjects who discontinued prior to their surgical intervention visit.
				Then, the indicator for maximum Dindo score ≥ grade III is defined as follows:
				1 = Yes, if the maximum of the Dindo scores as described above is $\geq$ grade III (i.e. score $\geq$ 3.1).
				0 = No, else if the maximum of the Dindo scores as described above is < grade III (i.e. score < 3.1).
				. = Missing, otherwise
				*Note: Prior to final database lock, a listing of all reported Dindo scores grade III or higher will be generated along with all complications reported on the corresponding form(s) and visit(s) and manually reviewed internally to ensure that the open-text specified complication corresponding to the reported Dindo score is reported as evident (i.e. response of "AE", "SAE") on the complication table(s). In addition, a masked data review by the AE Adjudication Committee will be performed to ensure that all reported Dindo scores of grade III and above are reasonable for the specified complication.
Indicator of excessive granulation tissue after 12 weeks	CRF-10, AE log	Binary	after 12 weeks through last visit	Through the timepoint of follow-up, based on the systematic collection of open-ended adverse events as reported on the AE log with an onset start date 12 weeks after the date of surgical intervention and based on the specific complications as reported on the evaluator (blinded) follow-up CRF-10 collected in 6-month intervals through 5 years, the indicator is defined as follows:
				1 = Yes, if granulation tissue is reported as evident (i.e. response of "AE", "SAE") on any of the complication tables as described above or on the AE log identified by the

				MedDRA coded preferred term "excessive granulation tissue" (case insensitive)
				0 = No, else if subject attended at least one post-operative visit 6 months or after and complication(s) of interest specified above are reported as "Not Evident" across all attended post-operative visits. Subjects with missing responses are included as long as the subject has at least one "Not Evident" response (assuming low missing response rate among attended visits).
				. = Missing, otherwise
Indicator of suture exposure after 12 weeks	CRF-10, AE log	Binary	after 12 weeks through last visit	Through the timepoint of follow-up, based on the systematic collection of open-ended adverse events as reported on the AE log with an onset start date 12 weeks after the date of surgical intervention and based on the specific complications as reported on the evaluator (blinded) follow-up CRF-10 collected in 6-month intervals through 5 years, the indicator is defined as follows: 1 = Yes, if suture exposure (anterior, posterior, introitus, or apexlocations) is reported as evident (i.e. response of "AE","SAE") on any of the complication tables as described
				above or on the AE log identified by the AE verbatim term containing "suture exposure" (case insensitive)
				0 = No, else if subject attended at least one post-operative visit 6 months or after and complication(s) of interest specified above are reported as "Not Evident" across all attended post-operative visits. Subjects with missing responses are included as long as the subject has at least one "Not Evident" response (assuming low missing response rate among attended visits).
				. = Missing, otherwise

Indicator of suture erosion after 12 weeks	CRF-13, AE log	Binary	after 12 weeks through last visit	Through the timepoint of follow-up, based on the systematic collection of open-ended adverse events as reported on the AE log with an onset start date 12 weeks after the date of surgical intervention and based on the specific complications as reported on the coordinator follow-up CRF-13 collected in 6-month intervals through 5 years, the indicator is defined as follows:
				1 = Yes, if suture erosion (urethra, bladder, ureter, rectum, bowel, or other specified location) is reported as evident (i.e. response of "AE", "SAE") on any of the complication tables as described above or on the AE log identified by the AE verbatim term containing "suture erosion" (case insensitive)
				0 = No, else if subject attended at least one post-operative visit 6 months or after and complication(s) of interest specified above are reported as "Not Evident" across all attended post-operative visits. Subjects with missing responses are included as long as the subject has at least one "Not Evident" response (assuming low missing response rate among attended visits).
				. = Missing, otherwise
Indicator of pelvic pain after 12 weeks	CRF-13, AE log	Binary	after 12 weeks through last visit	Through the timepoint of follow-up, based on the systematic collection of open-ended adverse events as reported on the AE log with an onset start date 12 weeks after the date of surgical intervention and based on the specific complications as reported on the coordinator follow-up CRF-13 collected in 6-month intervals through 5 years respectively, the indicator is defined as follows:
				1 = Yes, if pelvic pain or daily pelvic pain is reported as evident (i.e. response of "AE", "SAE") on any of the complication tables as described above or on the AE log identified by the MedDRA coded preferred term "pelvic pain" (case insensitive)

				
 
0 = No, else if subject attended at least one post-operative visit 6 months or after and complication(s) of interest specified above are reported as "Not Evident" across all attended post-operative visits. Subjects with missing responses are included as long as the subject has at least one "Not Evident" response (assuming low missing response rate among attended visits).
 
. = Missing, otherwise
 

Indicator of daily pelvic pain after 12 weeks	CRF-13, AE log	Binary	after 12 weeks through last visit	Through the timepoint of follow-up, based on the systematic collection of open-ended adverse events as reported on the AE log with an onset start date 12 weeks after the date of surgical intervention and based on the specific complications as reported on the coordinator follow-up CRF-13 collected in 6-month intervals through 5 years respectively, the indicator is defined as follows:
				1 = Yes, if daily pelvic pain is reported as evident (i.e. response of "AE", "SAE") on any of the complication tables as described above or on the AE log identified by the MedDRA coded term "pelvic pain" (case insensitive) and the AE verbatim term containing "daily pelvic pain" (case insensitive)
				
 
0 = No, else if subject attended at least one post-operative visit 6 months or after and complication(s) of interest specified above are reported as "Not Evident" across all attended post-operative visits. Subjects with missing responses are included as long as the subject has at least one "Not Evident" response (assuming low missing response rate among attended visits).
 
= Missing, otherwise
 

